7.13. Reporting Serious or Unexpected Adverse Events

Any SAE, irrespective of the relationship to study drug that occurs during the course of the study (from the first dose of study drug through Hospital Discharge, completion of Month 3 or early termination) will be reported on the eCRFs and SAE Report as soon as possible (within 24 hours after the site becomes aware of the event).

The Investigator is encouraged to discuss with the Sponsor's pharmacovigilance group any AE for which the issue of reportability is unclear or questioned.

An SAE Report should be prepared containing as much information as is available concerning the event so that a written report can be filed with appropriate regulatory authorities. If causality cannot be definitively assessed at the time of the SAE, it is important to notify Sponsor or its designees within the timelines stated above. When new significant information is obtained and the outcome and attribution of the event is known, the Investigator will communicate this information to the Sponsor or its designees and/or on the appropriate eCRFs. The relevant information will be provided in a timely manner to allow reporting to regulatory authorities within the required reporting period. Any SAE follow-up information requested by the Sponsor or its designees should be provided in a timely manner.

Additional information may be requested by the Sponsor or its designees to ensure that the initial reporting of SAEs is made to regulatory authorities within the requested timeframe. For a follow-up report to the regulatory authorities, the Sponsor or its designees may be required to collect further information for a detailed description and a final evaluation of the case, including copies of hospital reports, autopsy reports, or other relevant documents.

The Investigator, or Sponsor (or its designees) where applicable, will notify the relevant Institutional Review Board (IRB)/Independent Ethics Committee (IEC) of any SAEs and safety reports according to local regulation requirements.

7.14. Pregnancy

All pregnancies that occur during the study must be reported to the Sponsor and followed to conclusion. The outcome of each pregnancy must be reported.

Pregnancy alone is not an AE, nor is an induced elective abortion to terminate a pregnancy without medical reason. However, an induced therapeutic abortion to terminate a pregnancy due to complications or medical reasons must be reported as an SAE. The underlying medical

diagnosis for this procedure should be reported as the SAE term. A spontaneous abortion is always considered an SAE.

7.15. Discontinuation or Withdrawal

The criteria for study entry and enrollment must be followed explicitly. If a subject who does not meet the study entry and enrollment criteria is inadvertently enrolled and study drug administration has been started, the Investigator should consult with the Sponsor or its designees regarding the termination or continuation of the study drug administration.

If study drug is discontinued, the subject will continue in the study and undergo all study assessments per the protocol in order to provide the follow-up data needed for the analysis of the entire intent-to-treat population. Investigator or delegated site personnel will make the effort to collect the necessary data per protocol; however, if the subject is to be completely off the study per the discretion of the subject, Investigator, or Sponsor, study procedures for Early Termination should be completed.

7.15.1. Discontinuation of Study Drug

Discontinuation of study drug administration is defined as termination of the study drug administration without the intent to re-administer at a later time.

Subjects will discontinue the study drug administration in the following circumstances:

- The Investigator decides that study drug should be discontinued. If this decision is made due to a serious or intolerable AE or a clinically significant change in a laboratory value, the study drug is to be discontinued and appropriate measures taken (refer to [Section 7.1](#)). The designated Medical Monitor is to be alerted.
- The subject stops taking study drug. If this decision is made because the subject's condition has worsened, the surgical team (doctor) and the designated Medical Monitor should be alerted immediately.

7.15.2. Withdrawal from the Study

In the event that the subject, the subject's legal representative, the Investigator, or the Sponsor decides that the subject should be withdrawn from the study, all scheduled study assessments will be discontinued.

A subject may decide to withdraw from the study at any time. If a subject refuses to take study drug, the subject should be withdrawn from study participation. If the subject did take a portion of the study drug, the subject should remain in the study unless consent is withdrawn.

The Sponsor or its designees must be alerted if a subject is withdrawn from the study. A subject will be withdrawn from the study in the following situations:

- The subject or the subject's legal representative withdraws consent.
- The subject did not take any portion of study drug prior to surgery.
- The Investigator or the Sponsor, for any reason, stops the subject's participation in the study.

7.15.3. Discontinuation of Study Sites

Study site participation may be discontinued if the Sponsor, Investigator, or the IRB or IEC of the study site judges it necessary for any reason.

7.15.4. Institutional Review Board/Independent Ethics Committee Approval

The study protocol and Informed Consent Form (ICF), as well as any amendments, will be approved by an IRB or IEC as necessary for each study site.

7.15.5. Discontinuation of the Study

The study will be discontinued if the Sponsor judges it necessary for any reason.

QUALITY CONTROL AND ASSURANCE

Study training will be held for all sites prior to first subject enrollment. To ensure accurate, complete, and reliable data, the Sponsor or its representatives will do the following:

- Provide instructional material to the study sites, as appropriate.
- Conduct a start-up training session/Site Invitation Visit to instruct the Investigators and appropriate site staff. This session will give instruction on the protocol, the completion of the eCRFs, and study procedures.
- Make periodic visits to the study site.
- Be available for consultation and stay in contact with the study site personnel by mail, email, telephone, and/or fax.
- Review and evaluate eCRF data and use standard computer edits and/or source verification to detect errors in data collection.
- Conduct a quality review of the study database.

In addition, the Sponsor or its representatives may periodically check subject data recorded against source documents at the study site. The study may be audited by the Sponsor or its representatives, and/or regulatory agencies at any time. Investigators will be given notice before an audit occurs.

To ensure the safety of subjects in the study, and to ensure accurate, complete, and reliable data, the Investigator will keep records of laboratory tests, clinical notes, and subject medical records in the subject files as original source documents for the study. If requested, the Investigator will provide the Sponsor, applicable regulatory agencies, and applicable ethical review boards with direct access to original source documents and supporting study documentation.

PLANNED STATISTICAL METHODS

9.1. General Considerations

This study employs an adaptive clinical study design feature (interim analyses with possible sample size re-estimation). A comprehensive description of the statistical methods and analyses planned for this study will be provided in a Statistical Analysis Plan (SAP) prior to the planned interim analysis.

9.2. Determination of Sample Size

Although this study is not formally powered to detect a significant treatment effect, a sample size of 120 subjects is planned for enrollment/randomization and is considered adequate to establish proof-of-concept. The adaptive design of this study may allow for up to 200 total subjects enrolled at study completion.

9.3. Statistical Methods

Specific details about the statistical methods for all assessments, the treatment of missing data, and the method of control of the Type I error rate will be provided in the Statistical Analysis Plan (SAP).

9.3.1. Adhesions

Comparisons between the LB1148 and placebo groups with respect to change from baseline in extent and severity of intra-abdominal adhesions will be made using the Wilcoxon rank sum test.

9.3.2. Bowel Function

The primary efficacy analysis will be a time to event analysis (e.g., Cox proportional hazard model) with a main effect of treatment and stratified by surgery type (laparotomy versus minimally invasive approaches) and stoma (planned stoma versus no stoma). The p-values between the treatment groups will be evaluated using the Wald chi-square test. The magnitude of the treatment effect will be presented as the difference between the LB1148 and placebo arms in mean time to event (estimated by area under the Kaplan-Meier survival curve).

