Safety and tolerability will be assessed based on the incidence and severity of treatment emergent adverse events (AE), serious adverse events (SAEs), vital signs, clinical laboratory results. Specific safety sub-analyses will be performed to assess the safety of LB1148 in the following patient populations:

- patients who are on chemotherapy;
- patients with a venous port or catheter;
- patients with varicose veins and superficial vein thrombosis;
- patients with varying degrees of obesity;
- patients who are smokers;
- patients with varying degrees of renal function; and
- patient age groups, including 65-80 years old.

Statistical Methods:*Intra-Abdominal Adhesions:*

Comparisons between the LB1148 and placebo groups with respect to change from baseline in extent and severity of intra-abdominal adhesions will be made using the Wilcoxon rank sum test.

Bowel Function:

Bowel function analyses will be a time to event analysis (e.g., Cox proportional hazard model) with a main effect of treatment and stratified by surgery type (laparotomy versus minimally invasive approaches) and stoma (planned stoma versus no stoma). The p-values between the treatment groups will be evaluated using the Wald chi-square test. The magnitude of the treatment effect will be presented as the difference between the LB1148 and placebo groups in mean time to event (estimated by area under the Kaplan-Meier survival curve).

Interim Analyses:

An interim analysis of efficacy, safety, and tolerability will be performed after enrollment of approximately 50-60 subjects. Results from this interim analysis will permit a clearer determination of effect size and may trigger an increase in overall study sample size to up to 200 subjects enrolled.

TABLE OF CONTENTS

SPONSOR SIGNATURE	2
INVESTIGATOR'S SIGNATURE	3
SYNOPSIS	4
TABLE OF CONTENTS	10
LIST OF ABBREVIATIONS AND DEFINITIONS OF TERMS	14
1. INTRODUCTION	16
1.1. Summary	16
1.2. Post-Operative Ileus	17
1.3. Intra-abdominal Adhesion Formation and Impact	17
1.4. Rationale for Use of LB1148	18
2. STUDY OBJECTIVES AND ENDPOINTS	20
2.1. Study Objectives	20
2.1.1. Primary Objective	20
2.1.2. Secondary Objectives	20
2.1.3. Exploratory Objectives	20
2.2. Study Endpoints	20
2.2.1. Intra-Abdominal Adhesions	20
2.3. Bowel Function	21
2.3.1. Other Endpoints	21
2.3.2. Safety Endpoints	22
3. INVESTIGATIONAL PLAN	23
3.1. Overall Study Design and Plan	23
3.2. Rationale for Study Design, Control Group, and Perioperative Standardization	24

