4.2 Summarization of Data

Study results will be summarized in tabular format by treatment group, with descriptive statistics and/or in subject listings. In general, descriptive statistics for continuous variables will consist of subject count (n), mean, standard deviation (SD), minimum, first quartile, median, third quartile and maximum. Descriptive statistics for categorical variables will consist of subject counts and percentages.

All available safety and efficacy data will be included in data listings.

The efficacy analyses described in this Statistical Analysis Plan will be performed for the mITT (all efficacy endpoints) and PP Populations (primary efficacy endpoint and selected secondary efficacy endpoints), while the safety analyses will be performed for the Safety Population. All statistical tests will be 2-sided, with p-values considered nominal for this proof-of-concept study, although a p-value <0.05 will be highlighted. Unless otherwise specified, p-values will be reported to four (4) digits. No multiplicity adjustments will be performed.

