Selected time-to-event secondary efficacy endpoints (See Table in Section 11.5) will be analyzed using a stratified Cox PH model with treatment as the main effect, stratified by surgery type (laparotomy versus minimally invasive). In addition to surgery type, a categorical age (<65 years, ≥ 65 years) will be included. Nominal p-values will be reported. Comparison of treatment groups and assessment of the significance of the parameter estimates for surgery type will be made using the Wald chi-square test.

In addition to the semi-parametric Cox PH model, non-parametric Kaplan-Meier survival curves will be produced for the two treatment groups and compared using a stratified log-rank test; results from this test will be considered nominal/hypothesis-generating in nature. The number of hours to each endpoint will be presented in summary tables with descriptive statistics for the mITT (all variables selected) and PP populations (POI, GI2, and GI3 variables only).

Those endpoints defined as yes/no variables will be analyzed using a chi-square test for homogeneity of proportions.

All findings will be presented in subject listings for the mITT population, including calculated time to event efficacy variables.

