11.3 Exploratory Endpoints

The exploratory endpoints are:

- Hospital LOS (number of days in the hospital, evaluated in hours) will be measured first by time to discharge order is written. The time will start at time of surgical closure and run until discharge order is written.
- Pain values, evaluated using
 - Values recorded from the NPRS
 - Analgesia consumption, including totals for opioid use and morphine equivalents
 - See Section 15 APPENDIX A for conversion guidelines
- The number of subjects with recorded bowel obstructions (Listing only)
 - AE Preferred Terms having the phrase "bowel obstruction" in them e.g., small bowel obstruction
- The number of subjects with a hospital re-admission
- Blood product transfusion volume on the day of surgery (Listing only)

The following LOS parameters will also be evaluated:

- Time from surgical closure to actual discharge
- Time from surgical closure to standard discharge (Listing only) The time will start at time of surgical closure and run until all four criteria for discharge have been met. The criteria are:
 - Passage of stool
 - Ability to tolerate solid food and drink comfortably
 - Adequate oral analgesia, and
 - Subject's willingness to be discharged

Selected time-to-event endpoints (See Table in Section 11.5) will be analyzed using a stratified Cox PH model with treatment as the main effect, stratified by surgery type (laparotomy versus minimally invasive). Comparison of treatment groups and assessment of the significance of the

parameter estimates for surgery type will be made using the Wald chi-square test. In addition to the semi-parametric Cox PH model, non-parametric Kaplan-Meier survival curves will be produced for the two treatment groups and compared using a stratified log-rank test. The number of hours to each endpoint will be presented in summary tables with descriptive statistics for the mITT and PP populations.

Pain assessments will be collected daily from surgery (Day 0) through post-operative Day 14 (or for as long as the patient remains hospitalized), at hospital discharge, and at the second surgery.

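### The SAP omits, without explanation, the protocol's bowel-function effect measure (difference in Kaplan-Meier mean time) and does not say how censored subjects enter its tables of hours

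*Protocol*

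**What the plan says.** The protocol commits to one measure of magnitude for bowel function. Section 9.3.2 names the "difference between the LB1148 and placebo arms in mean time to event (estimated by area under the Kaplan-Meier survival curve", and the Statistical Methods part of the synopsis repeats it. Section 9.3 leaves to the SAP "Specific details about the statistical methods for all assessments, the treatment of missing data" and type I error control.

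SAP 11.2.2 says selected time-to-event endpoints "will be analyzed using a stratified Cox PH model with treatment as the main effect", with Wald tests and nominal p-values. It adds that "non-parametric Kaplan-Meier survival curves will be produced for the two treatment groups and compared using a stratified log-rank test". The only output on the hours scale is this: "The number of hours to each endpoint will be presented in summary tables with descriptive statistics". SAP 4.2 defines that content: "descriptive statistics for continuous variables will consist of subject count (n), mean, standard deviation (SD), minimum, first quartile, median, third quartile and maximum", by treatment group. SAP 11.3 repeats the approach for the discharge endpoints.

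The table in SAP 11.5 has columns for Cox PH, Kaplan-Meier and Other (frequency tables or listings). SAP 11.4 censors death without the event, loss or withdrawal without the event, and no event within 14 days all at Study Day 14. Its footnote covers GI2, GI3, bowel movement, liquid diet, solid diet, discharge order written and actual discharge. The SAP's revision table does not mention removing the protocol's measure.

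**The concern.** The secondary objectives for GI2, GI3 and resolution of POI are worded in hours, and the protocol chose an effect measure in hours to match. Under the SAP as written, no between-arm contrast on that scale, and no interval for one, is planned. SAP 11.2.2 does not name a hazard ratio with a confidence interval either; it commits to Wald tests. For liquid diet, the 11.5 table gives Cox as No and Kaplan-Meier as Yes, so even a model-based estimate is absent.

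The descriptive tables could fill part of the gap, but only if the reader knows what was done with subjects who had not reached the endpoint by Day 14. If they are left out, the table describes achievers only. An effect that works by reducing the number of non-achievers would then be understated or would disappear. Because the plan treats its p-values as nominal, the estimates carry most of the information, so the gap is worth closing.

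**Working it through.** The documents give no effect size, event count or power figure based on this measure, so there is nothing of the plan's own to reproduce. The check has two parts: the text, then what the unspecified choice could do to the numbers.

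**1. Text side by side**

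| Item | Protocol synopsis and 9.3.2 | SAP 11.2.2 and 11.5 |
|---|---|---|
| Test | Wald test from a Cox-type model | Wald test from Cox PH; stratified log-rank |
| Effect size | Difference in Kaplan-Meier mean time | None named in hours |
| Interval in hours | Not stated | None |
| Censored subjects in hours tables | Not addressed | Not addressed |
| Truncation time for the mean | Not stated | Not applicable |

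**2. When a plain mean is adequate**

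Suppose every non-event is censored at one common time τ. The Kaplan-Meier curve before τ is then the observed fraction still without the event, and its area to τ equals the plain mean of min(T, τ). With τ = 14 × 24 = 336 h, 2,000 simulated arms of 15 gave a largest gap of about 1e-13 h. For example, take 14 achievers averaging 72 h (assumed) and one non-achiever:

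- non-achiever counted at 336 h: (14 × 72 + 336)/15 = 89.6 h, which is the restricted mean;
- non-achiever left out: 72 h.

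**3. Effect on the treatment difference**

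Assume achievers average 96 h in both arms. The restricted mean is (1 − p) × 96 + p × 336, where p is the proportion of non-achievers.

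- p = 10% on placebo, 5% on LB1148: 120 h and 108 h, difference -12 h. Achievers only: 0 h.
- p = 20% and 10%: 144 h and 120 h, difference -24 h. Achievers only: 0 h.

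A less extreme case uses lognormal times with a time ratio of 0.75 (all inputs assumed):

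| Control median, log-SD | Non-events, placebo / LB1148 | Restricted mean difference | Achievers-only difference | Shrinkage |
|---|---|---|---|---|
| 72 h, 0.6 | 0.5% / 0.1% | -21.1 h | -20.1 h | 5% |
| 72 h, 0.9 | 4.4% / 2.1% | -22.4 h | -17.1 h | 24% |
| 96 h, 0.6 | 1.8% / 0.5% | -27.6 h | -24.7 h | 11% |
| 96 h, 0.9 | 8.3% / 4.3% | -26.7 h | -18.5 h | 31% |
| 144 h, 0.6 | 7.9% / 2.9% | -36.7 h | -28.0 h | 24% |
| 144 h, 0.9 | 17.4% / 10.4% | -31.4 h | -19.3 h | 39% |

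Shrinkage is 1 minus the ratio of the two differences, for example 1 − 19.3/31.4 = 39%.

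**4. Early losses under SAP 11.4**

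Moving losses to Day 14, rather than censoring at last contact, raises an arm's mean. With median 96 h, log-SD 0.6 and losses spread over the first 96 h (assumed), the true restricted mean is about 113 h. The Day 14 rule gives 117.6, 125.4 and 135.6 h for 3%, 7% and 13% losses. Censoring at the time of loss gives 112.9, 113.2 and 113.1 h.

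**5. Precision**

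SAP 4.3 expects at least 30 randomized, so about 15 per arm at 1:1. In the 96 h, 0.6 scenario, simulation puts the SDs of the restricted times at about 68 h and 54 h. The 95% half-width is 1.96 × √(68²/15 + 54²/15) ≈ 44 h, against a difference of about 27 h.

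**The case against.** The strongest reply is that little is lost. The SAP still reports mean, median and quartiles of hours by arm and plots the curves. Under the common censoring point in 11.4, an ordinary mean with non-achievers counted at that point is the Kaplan-Meier area, as step 2 shows. A reader might infer that the SAP leaves no valid effect in hours, or that its means are biased low. The documents support neither: the first fails by that identity, and the second holds only if non-achievers are excluded, which the SAP does not say.

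A reader might also infer that these data are meant to size a later bowel-function trial. SAP 4.3 and 11.1.1 say that of the adhesion endpoint only.

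Protocol 9.3.2 is itself partly out of date. It still labels bowel function as primary and stratifies by stoma, although Amendment 4 made adhesions primary and Amendment 5 restricted entry to planned-stoma subjects. Protocol 9.3 also hands details to the SAP.

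These points limit the importance but do not answer the omission. Delegating details is not the same as dropping a named measure, and neither the SAP text nor its revision table records a decision to do so. The tables contain no contrast or interval, and whether they equal the Kaplan-Meier mean depends on a rule that is not written down.

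**Conclusion.** The point holds as an unexplained mismatch between protocol and SAP, together with an unspecified rule for censored subjects in the tables of hours. Depending on that rule, the descriptive difference could equal the protocol's measure or, in the assumed lognormal scenarios, be about 5% to 39% smaller. It could show no effect at all when the arms differ only in the share of non-achievers. These sizes rest on assumed event times and non-achievement rates, because the documents give none.

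The 336 h horizon is also an assumption. SAP 4.4.2 counts Day 1 from the first split dose for start and end dates but uses the protocol's visit names elsewhere (surgery is Day 0), and 11.4 speaks both of 14 days of surgery and of Study Day 14.

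Priority is modest. The endpoints are secondary, nothing is powered on them, and a restored estimate would be wide at this sample size.

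**What to change.** In SAP 11.2.2, for GI2, GI3, bowel movement, liquid diet and solid diet (the bowel-function endpoints in the 11.4 footnote), report restricted mean time to 14 days after surgical closure by arm, and the difference with a 95% CI, stratified by surgery type. The two discharge endpoints in 11.3 may be added, although protocol 9.3.2 does not require it. POI within 14 days should not be included by default: it has a Kaplan-Meier Yes in 11.5 but is not in the 11.4 censoring list. If the sponsor prefers not to restore the measure, record its removal and the reason.

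Also:

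- define the horizon from surgical closure instead of Study Day 14;
- state how censored subjects enter the descriptive tables, and label any achievers-only summary as among subjects with the event;
- report by arm the number of deaths and early losses set to Day 14, with a sensitivity analysis that censors losses at last contact.

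The cost is a few SAP sentences and one extra output per endpoint from curves already planned, plus the sensitivity run. Sample size, alpha and data collection do not change.
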